products (eg, Astagraf XL). The MeltDose technology decreases a drug's particle size to the smallest possible units as single molecules. Drug particle size critically affects drug dissolution and absorption; if particle size is smaller, the surface area of the drug increases and the drug will be dissolved more quickly, resulting in better absorption. Results of the MeltDose technology are increased absorption and bioavailability associated with LCPT tablets compared with other extended-release and IR tacrolimus formulations currently available. Phase 1 and phase 2 trials confirmed that LCPT enables broader absorption throughout the gastrointestinal tract and sustains consistent tacrolimus concentrations⁴. In addition, LCPT showed a lack of diurnal variability common with other formulations.

Phase 2 trials of de novo and stable kidney and liver recipients showed a steadier and more consistent concentration-time profile over 24 hours, with reduced peak and peak-to-trough fluctuations for LCPT compared to IR-Tac, increased bioavailability of ~30%, and comparable efficacy and safety profiles. A robust correlation between the area under the curve at 24 hours and the minimum concentration was also shown, indicating that therapeutic drug monitoring of minimum concentration as a measure of tacrolimus exposure can be applied to LCPT. A phase 3 conversion trial showed that LCPT had noninferior efficacy and comparable safety profile to IR-Tac, with lower doses (~20% lower than IR-Tac overall and 30% lower in white patients) of LCPT⁵.

Hypothesis

African American renal transplant recipients that receive Envarsus will have less tubular injury and calcineurin inhibitor toxicity compared with patients that receive tacrolimus IR.

Study Type/Design

This is a case control study where a prospective cohort will be started de novo on Envarsus at the time of renal transplantation.

Endpoints

Primary endpoint is to determine the rate of calcineurin inhibitor toxicity as measured by surveillance kidney biopsies.

Secondary endpoint is to determine the rate of development of donor specific antibodies of the patients treated with Envarsus vs the patients treated with immediate release tacrolimus.

Patient Recruitment

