We will prospectively consent 100 African American patients that will be receiving kidney transplants at our center. This cohort will be matched with a retrospective cohort of African American renal transplant recipients who received renal transplant and were treated with immediate release tacrolimus.

Exclusion criteria will include patients that are not African American and patients that are younger than 18 years old.

Inclusion Criteria

1. African American race

2. Adult renal transplant recipients (≥ 18 y/o)
3. Previous adverse reaction or contraindication to the use of tacrolimus

Exclusion Criteria

1. Non African American race
2. Less than 18 y/o (pediatric patients)
3. Recipients of liver and small bowel transplants
4. Adverse reaction to tacrolimus

Statistical analysis:

Data will be analyzed using standard statistical methods using chi square test, students T-square test, kaplan-meyer curve. No statistical analysis has been performed to achieve adequate power as this an observational study.

Treatment Overview

Screening will be performed by the Principal Investigators during the kidney transplant evaluation clinics, during the wait list kidney transplant evaluation clinic and prior to a schedule kidney transplant surgery.

Dosage and Administration of Envarsus XR

Patients enrolled in the prospective arm of the study will be started on Envarsus XR at 0.17mg/kg. The dose will be targeted to achieve a tacrolimus level between 8-10 ng/mL.

The tacrolimus level will be modified depending on the results of the surveillance biopsy, BK and CMV viruses, and donor specific antibody studies.

Laboratory Testing and Study Schedule

Schematic diagram of data that will be obtained during study:

Data to be obtained at time 0 on the prospective and retrospective cohort

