1. BMI

2. Weight
3. Sex
4. Reason for chronic kidney disease
5. Induction agent
6. Crossmatch results
7. Type of donor
8. Donor age
9. Donor sex
10. Donor end creatinine
11. Donor's biopsy result if available

Data to be obtained at time 1 month, 3 month, 6 month and 12 month on the prospective and retrospective cohort

1. Creatinine level
2. Proteinuria
3. Tacrolimus level
4. Diabetes
5. Blood pressure
6. BK virus serum
7. CMV virus PCR
8. Donor specific antibody
9. Biopsy results (at 3 and 12 months surveillance and any other additional for cause biopsy that the patient may have had)

10. Infections
11. Hospital admissions
12. Blood transfusions (if any)

Patient Monitoring and Evaluation

Patients will have a kidney biopsy at time 0 (at the time of implantation and prior to reperfusion), 3 months and 12 months. If at any other time it is clinically necessary to perform another biopsy, it will be performed.

Potential Pitfalls and Contingencies

If a patient develops side effects that are attributed to tacrolimus, then the patient may have to be switched to another immunosuppression regimen.

References

1. Prograf [prescribing information]. Northbrook, IL: Astellas Pharma US, Inc; September 2013.

3. Bechstein WO. Neurotoxicity of calcineurin inhibitors: impact and clinical management. *Transpl Int.* 2000;13(5):313-26.

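### The baseline list omits recipient age, pre-transplant diabetes and blood pressure, HLA mismatch, sensitisation history and pre-transplant donor specific antibody, so control of confounding against the retrospective cohort is incomplete

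*Combined protocol and SAP*

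**What the plan says.** The protocol compares 100 consented Envarsus patients with a retrospective cohort on immediate-release tacrolimus. Patient Recruitment says the cohorts will be matched but names no matching variables. The primary endpoint is calcineurin inhibitor toxicity on surveillance biopsy, and the secondary endpoint is the rate at which DSA develops. Statistical analysis names the chi-square test, a t-test and Kaplan-Meier curves, with no adjusted method.

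Laboratory Testing and Study Schedule gives two numbered lists, each for both cohorts:

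- "Data to be obtained at time 0 on the prospective and retrospective cohort": BMI, weight, sex, cause of kidney disease ("4. Reason for chronic kidney disease"), induction agent, crossmatch ("6. Crossmatch results"), donor type, donor age, donor sex, donor end creatinine, and the donor's biopsy if there is one.
- "Data to be obtained at time 1 month, 3 month, 6 month and 12 month on the prospective and retrospective cohort": 12 items, among them diabetes (item 4), blood pressure ("5. Blood pressure") and DSA (item 8).

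Exposure begins before the second list does, because "a prospective cohort will be started de novo on Envarsus at the time of renal transplantation". Recipient age appears only as an eligibility threshold, as in "2. Adult renal transplant recipients (≥ 18 y/o". Patient Monitoring and Evaluation adds a baseline biopsy: "Patients will have a kidney biopsy at time 0 (at the time of implantation and prior to reperfusion), 3 months and 12 months".

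**The concern.** Without randomisation, the two cohorts can be made comparable only through variables recorded before treatment starts. Several obvious candidates are missing from the time-0 list. Diabetes, hypertension and early ischaemic injury are plausible alternative causes of the changes read as calcineurin inhibitor toxicity. HLA mismatch and earlier sensitisation are natural determinants of DSA. The eligibility criteria exclude neither sensitised recipients nor those with a previous kidney transplant, so these factors can vary within and between cohorts.

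Month-1 diabetes and blood pressure cannot stand in for baseline values. By then they may partly be effects of tacrolimus or co-medication, and adjusting for them could remove part of a real formulation effect or introduce bias. As listed, diabetes present before transplant also cannot be separated from diabetes that began afterwards.

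For the secondary endpoint there is a problem of definition as well as confounding. Development of antibody implies absence at the start, yet DSA is first listed at month 1.

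**Working it through.** The documents give no event rate, effect size, alpha or power, so there is no stated figure to reproduce. The first step is a check of the two lists.

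| Factor | Time 0 | Months 1–12 | Nearest item collected at or near baseline |
|---|---|---|---|
| Recipient age | no | no | none; eligibility threshold only |
| Diabetes | no | item 4 | reason for kidney disease |
| Blood pressure | no | item 5 | reason for kidney disease |
| HLA mismatch | no | no | none |
| Panel reactive antibody, previous transplant | no | no | crossmatch |
| DSA | no | item 8 | crossmatch |
| Cold ischaemia time | no | no | donor type, donor end creatinine |
| Delayed graft function | no | no | month-1 creatinine |

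**How much could one missing factor matter?** Every input below is an assumption except the 100 Envarsus patients. The size of the comparator cohort is not stated and is set at 100; the test is a two-sided 5% chi-square without continuity correction; there is no true formulation effect. One unrecorded binary factor has prevalence u in a cohort and multiplies the outcome risk p0 by RR:

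- Cohort rate: r = p0 × [1 + u × (RR − 1)], written r1 for Envarsus and r0 for controls; d = r0 − r1.
- Probability of a significant result: Φ((d − 1.96·s0)/s1) + Φ((−d − 1.96·s0)/s1), where m = (r1 + r0)/2, s0 = √(2m(1 − m)/100) and s1 = √([r1(1 − r1) + r0(1 − r0)]/100).

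The grid was p0 = 15% or 30%, RR = 1.5, 2 or 3, and prevalence 30% in the Envarsus cohort against 40% or 50% in controls.

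- Low end (p0 15%, RR 1.5, 30% v 40%): r1 = 0.15 × 1.15 = 17.25%, r0 = 0.15 × 1.20 = 18.0%. The false difference is 0.75 points, the ratio 0.96 and the false-positive rate 5.2%.
- Intermediate (p0 15%, RR 3, 30% v 50%): r1 = 0.15 × 1.6 = 24%, r0 = 0.15 × 2.0 = 30%. The false difference is 6 points, the ratio 0.80 and the false-positive rate 15.9%.
- High end (p0 30%, RR 3, 30% v 50%): r1 = 0.30 × 1.6 = 48%, r0 = 0.30 × 2.0 = 60%. The false difference is 12 points, the ratio 0.80 and the false-positive rate 39.8%. This case implies a 90% risk in patients with the factor (0.30 × 3), so it is an outer bound.

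**Direction.** Suppose DSA arises in 25% of sensitised and 8% of unsensitised recipients (assumed). With 40% of controls and 20% of Envarsus patients sensitised, controls have 0.40 × 25% + 0.60 × 8% = 14.8% and Envarsus patients 0.20 × 25% + 0.80 × 8% = 11.4%. That is a false 3.4-point benefit. Exchanging the two prevalences gives a false 3.4-point harm. With 100 per cohort the standard error is √[(0.148 × 0.852 + 0.114 × 0.886)/100] = 4.8 points, so this bias is about 0.7 of a standard error (3.4/4.8).

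**Pre-existing antibody.** Let q be the proportion with DSA before transplant and d* the true incidence in the rest. If pre-existing antibody persists and is counted, the apparent rate is q + (1 − q)d*. With equal d* in both cohorts, the false difference is (q0 − q1)(1 − d*). At d* = 8% each point of imbalance in q becomes 0.92 points of apparent effect, or less if some antibody disappears before it is tested.

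**The case against.** The best defence is that the plan collects a good deal. Both cohorts have reason for kidney disease, induction agent, crossmatch, donor type, donor age and donor creatinine at time 0. Follow-up adds tacrolimus level, BK virus, CMV, transfusions and for-cause biopsies. The implantation biopsy helps separate donor-derived lesions from later ones. The missing items are probably in the transplant record, and nothing in Patient Recruitment confines matching to the listed variables.

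Much of this stands, and it rules out several stronger readings that a reader might infer:

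- *That sensitisation is never collected.* Crossmatch is a partial, donor-specific measure of it. What is missing is panel reactive antibody, previous transplant and pre-transplant DSA.
- *That the data cannot separate formulation from the main other causes of either endpoint.* The documents do not rank those causes, and several are recorded.
- *That the bias could never be removed later.* If the items are in the record they can still be abstracted; recipient age in particular must be known to establish eligibility.
- *That the omissions favour Envarsus.* Nothing in the documents indicates a direction, and several imbalances may cancel as well as add.
- *That delayed graft function is an omitted baseline confounder.* It arises after transplantation, when Envarsus has already started, so the reasoning that rules out month-1 diabetes applies to it too.

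What does not stand is the idea that the listed items suffice. Reason for kidney disease misses diabetes as a comorbidity and gives no blood pressure. Crossmatch does not record HLA mismatch or the breadth of sensitisation, and the plan does not say how it would be used. The biopsy is taken before reperfusion, so it cannot show later early injury, and the protocol does not say that it exists for the retrospective cohort.

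**Conclusion.** The concern holds as a gap in specification. If the two lists are followed as written, no matching or adjustment based on them can include recipient age, pre-transplant diabetes or blood pressure, HLA mismatch, panel reactive antibody, previous transplant or cold ischaemia time, and new DSA cannot be reliably told from old. The collected items reduce the problem without closing it.

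The omissions can be read directly from two complete, numbered lists. The consequence cannot be sized from the documents. On the assumed inputs it runs from a negligible effect to a serious one, in either direction, and a larger sample would not remove it. Without the variables the investigators could not tell where in that range the study lies. The lists should be extended, but the omissions alone do not show that the comparison is uninformative.

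**What to change.** For both cohorts, add to the time-0 list: recipient age, pre-transplant diabetes, pre-transplant blood pressure, HLA mismatch, panel reactive antibody, previous transplant, cold ischaemia time, and pre-transplant DSA where recorded. Then:

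- Name the pre-transplant values, not diabetes or blood pressure from month 1 onwards, as variables in the matching and in an adjusted comparison reported alongside the chi-square test, for example logistic regression or a propensity score. Collecting the items achieves nothing if the analysis stays unadjusted and the matching unspecified. With 100 Envarsus patients the number of events will limit how many covariates a regression can carry, so choose them in advance.
- Count as DSA development only antibody absent before transplant, and state how patients with no recorded pre-transplant result are handled.
- Record delayed graft function at month 1 as a post-transplant event, report it by cohort, and use it only in a sensitivity analysis.

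The cost is a longer chart abstraction form and some missing values in the historical cohort, which should be reported by item. No new test or visit is needed.

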1. BMI

2. Weight
3. Sex
4. Reason for chronic kidney disease
5. Induction agent
6. Crossmatch results
7. Type of donor
8. Donor age
9. Donor sex
10. Donor end creatinine
11. Donor's biopsy result if available

Data to be obtained at time 1 month, 3 month, 6 month and 12 month on the prospective and retrospective cohort

1. Creatinine level
2. Proteinuria
3. Tacrolimus level
4. Diabetes
5. Blood pressure
6. BK virus serum
7. CMV virus PCR
8. Donor specific antibody
9. Biopsy results (at 3 and 12 months surveillance and any other additional for cause biopsy that the patient may have had)

10. Infections
11. Hospital admissions
12. Blood transfusions (if any)

Patient Monitoring and Evaluation

Patients will have a kidney biopsy at time 0 (at the time of implantation and prior to reperfusion), 3 months and 12 months. If at any other time it is clinically necessary to perform another biopsy, it will be performed.

Potential Pitfalls and Contingencies

If a patient develops side effects that are attributed to tacrolimus, then the patient may have to be switched to another immunosuppression regimen.

References

1. Prograf [prescribing information]. Northbrook, IL: Astellas Pharma US, Inc; September 2013.

3. Bechstein WO. Neurotoxicity of calcineurin inhibitors: impact and clinical management. *Transpl Int.* 2000;13(5):313-26.
